Initial Online Screening. Parents responding to our recruitment materials (see section D: Recruitment Methods) will complete an online survey via UO Qualtrics to assess initial eligibility criteria. Parents will be asked to confirm that they are 18+ years of age, that they reside in Oregon, that they have at least partial custody of a preschool aged child (3-6 years old), that neither they nor their child has any known developmental disability, that they are proficient in English, and that they have the internet access needed to participate in an online remote telehealth intervention. We will also provide the scheduled weekly day and time of group therapy sessions so that parents can verify and confirm they will be able to participate. After confirming all of the above, parents will complete a self-report questionnaire evaluating parents' emotion dysregulation and a screener for drug and alcohol problems. To participate in the study, parents must endorse a score of >88 on the Difficulties with Emotion Regulation Scale (DERS) and meet a cutoff of 2 positive answers on an adapted version of the CAGE-AID screener for drug and alcohol problems, which asks about past (past 5 years) but not current (not in the past 12 months) substance use. Parents who pass the initial online screening will be asked to provide their contact details so that a project coordinator can schedule a clinical intake with them. Parents who do not pass the initial online screening will be thanked for participating and informed that they do not match the eligibility requirements. See Appendix E. Online Screening Script.

Clinical intake. Parents who meet screening criteria will be contacted and invited for the remotely conducted clinical intake (see Appendix F. Intake Scheduling Script). During intake scheduling, the project coordinator will ask for participating parents' permission to be contacted via email, text and phone. The clinical intake will be conducted via a HIPAA compliant teleconference platform (Zoom), and a Zoom link will be emailed to the parent, using an encrypted email service (Hushmail). The purpose of the clinical intake is to: 1) formally determine eligibility and 2) characterize current parental mental health diagnoses. A trained intake clinician will consent parents to the intake process and ask

them to provide consent for the remainder of the study components (for details see section E. Informed Consent Process and Appendix A. Informed Consent Form).

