- A. The Difficulties with Emotion Regulation Scale (DERS; Gratz & Roemer, 2004) is a 36-item selfreport measure used to assess adult emotion dysregulation. Items are rated on a scale of 1 to 5, with higher scores indicating higher levels of dysregulation. The measure is comprised of six subscales: lack of emotional awareness, lack of emotional clarity, limited emotion regulation strategies, difficulties with impulse control, difficulties engaging in goal-directed behavior, and nonacceptance of emotional responses.
- B. CAGE-Adapted to Include Drugs (CAGE-AID; Brown & Rounds, 1995) is a 4-item screener for alcohol and drug use. Items are scored 0 for "no" and 1 for "yes" responses. Higher scores are an indication of greater alcohol and drug problems. A total score of 2 or greater is considered clinically significant. The original measure focuses on lifetime use. For the purposes of this study, participants will be asked to answer for the time period in the past 5 years, but not in the past year.
- C. Demographic questionnaire. Standard questions for assessing parent age, child age, parent gender, child gender, parent marital/relationship status, educational background, sexual orientation, number of people in household, number of children, race, ethnicity, socioeconomic status, and religious affiliation.
- D. The Patient Health Questionnaire depression module (PHQ-9; Kroenke, Spitzer, & Williams, 2001) is a 9-item self-report questionnaire in which participants rate how often depressive symptoms have bothered them in the past 2 weeks on a scale of 0 (Not at all) to 3 (Nearly every day). Scores are summed for a total score ranging from 0 to 27 with higher scores indicating higher levels of depressed mood.
- E. The Peabody Picture Vocabulary Test (PPVT-V Q-Global; Dunn & Dunn, 2007) form A is a forcedchoice format test of receptive vocabulary that provides an estimate of verbal cognitive ability of English-speaking adults and children. Participants are shown a page containing four drawings (in color) laid out in a 2-by-2 grid. Participants are then asked to point to the picture that corresponds to a word said by the experimenter. The task consists of 228 numbered items which are grouped into 19 sets of 12 items each and items increase in difficulty across the task. Items are administered

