until the participant commits 8 or more errors in a given set. Standardized scores on this measure range from 20-160. The Q-Global administration is a web-based version to administer the test.

- F. Structured Clinical Interview for DSM-5 (SCID-5; First, Spitzer, Gibbon & Williams, 2015). The SCID-5 will be used as the diagnostic measure during the intake to assess parents' potential mental health disorders, including substance use disorders. Substance use disorder modules will assess for current (past 12 months) and past (past 5 years) of the following DSM 5 defined disorders: alcohol, cannabis, hallucinogenic, inhalant, opioid, sedative/hypnotic/anxiolytic, and stimulant.
- G. The Hamilton Anxiety Scale (HAM-A; Hamilton, 1969) is a 14-item self-report measure that assesses physical symptoms of anxiety. Subjects rate the severity of symptoms ranging from 0 (Not present) to 4 (Very Severe). Scores are summed for a total score ranging from 0 to 56, with higher scores indicating higher levels of anxiety.
- H. The Aggregated Drug Craving Scale (ADCS; Costello et al., 2020) is an adaptation of the Penn Alcohol Craving Scale (PACS; Flannery et al., 1999) aimed at measuring a broad range of substance craving. The measure includes five items that assesses intensity, frequency, and duration of craving along with ability to resist substance use if it was available, and it asks responders to give an average craving rating for the past week. The response ranges from 0 to 6 for each item and higher scores indicate greater cravings.
- I. The DBT Ways of Coping Checklist (DBT-WCCL; Neacsiu et al., 2010) is a 38-item self-report questionnaire which measures the frequency of DBT Skills use.
- J. The Weekly Assessment of Child Behavior (WACB, Forte et al., 2012) is a brief 9-item parent-report measure in which parents rate (on a Likert scale of 1-7) how often their child engages in positive behaviors on a weekly basis. The measure is based on the positive opposites of behaviors measured by the Eyberg Child Behavior Inventory (ECBI) and yields two scales: Intensity and Need-to-Change. The measure has demonstrated strong convergent validity with other established measures of child behavior problems.

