- P. The Coping with Children's Negative Emotions Scale (CCNES; Fabes, Eisenberg & Bernzweig, 1990) assesses parental self-report of emotion socialization practices. Parents are presented with 12 vignettes describing scenarios in which their children exhibit distress. Parents rate (on a Likert scale of 1-7) the likelihood they would engage in 6 potential parental responses to these situations, with each corresponding to 6 subscales: distress reactions, punitive reactions, minimization, expressive encouragement, emotion-focused reactions and problem-focused reactions. The first three can then be summed into an Invalidating/Unsupportive composite and the latter three can be summed into a Validating/Supportive composite.

- Q. Skill Use Diary Card. A diary card developed for this study will be used to assess parents' weekly use of specific DBT and parenting skills, both as a study measure of treatment dosage and for treatment purposes. Parents are asked to circle days of the week in which they used each skill. Additionally, they are asked if DBT Skills were used in a parenting or a non-parenting context. Diary cards also include an additional question that assesses for suicidal thoughts over the past week.
- R. The Client Satisfaction Questionnaire (CSQ-8; Attkisson & Zwick, 1982) will be used to assess acceptability of the intervention. It is a brief 8-item self-report measure in which clients are asked to rate (on a Likert scale of 1-4) their satisfaction with the intervention.
- S. Qualitative Exit Interview. A semi-structured exit interview will be used to evaluate parents' satisfaction with the intervention, challenges they experienced completing the intervention, their use of DBT/Parent training skills, and suggestions they have for improving the intervention delivery. Interviews will be video recorded so that representative quotes and themes can be identified.

Analyses

We will conduct multiple analyses to evaluate how, when, why, and to what extent the DBT Skills +PT intervention was effective in changing parents' mental health and/or parents' parenting quality and/or children's mental health and behavior. All data will be de-identified and all findings from our analyses will be reported anonymously.

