Aim 1. Determine feasibility, acceptability and implementation. Three types of feasibility will be examined. Feasibility of recruitment will be assessed by examining the number of participants meeting eligibility on the initial online screener and the number of participants meeting eligibility following the clinical intake. Feasibility of measurement tools will be assessed by calculating the average time taken by participants to complete the online Qualtrics questionnaires, and the average percentage of missing data from the online questionnaires. Feasibility of the intervention will be evaluated by calculating the average number of sessions attended by parents.

Acceptability will be examined by averaging the total scores obtained from the Client Satisfaction Questionnaire (CSQ-8). In addition, using qualitative thematic analyses, we will report on data collected during the exit interview, identifying overall themes about the intervention that emerge from parents' comments.

We will examine implementation by calculating the average daily number of DBT and parenting skills parents report using each week on their diary card (averaged across parents) and comparing these to skill use reported in other published research (ex. 7-8 DBT skills per week; Gamache [name] et al., 2017). We will primarily report data for Aim 1 at an aggregated group level. We may also include de-identified information at the individual level in the form of quotes from parents' exit interviews.

Aim 2. Evaluate pre-post and weekly changes. We will examine pre-post changes for the primary outcomes of DBT Skill use (DBT-WCCL), parental emotion dysregulation (DERS), parenting stress (PSI) and parenting quality (PS, CCNES). Pre-post change scores will also be calculated for the secondary outcomes of child internalizing and externalizing behaviors (CBCL), child emotion regulation (ERC), parent mental health symptoms (HAM-A, PHQ-9, ADCS). Pre-post change scores will be compared to the clinical trial literature base for DBT and parent training interventions which often use the same measures and for which expected change scores are established. Additionally, based on post-intervention reports during the SCID 5 diagnostic interview, the percentage of parents reporting sustained recovery (vs relapse) from substance use disorder will be calculated and reported.

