Participants. We intend to recruit and conduct intakes with approximately 18 parents, enroll up to 15 eligible parents in DBT+PT, so as to reach our target of 12 parents who complete at least 4 sessions. This attrition rate is based on our lab's prior experience providing DBT Skills to a parent population. Participating parents will be split into three DBT Skills +PT groups that are run at different times over the course of the year. Recruitment efforts will take place twice over the course of the year to facilitate this.

To participate, parents must be 18+ years of age and reside in Oregon, have at least partial custody of a 3-6 year old child, neither parent nor child may have any known developmental disability, and the parent must be proficient in English, as our laboratory is unable to conduct the clinical intake, assessments, and DBT Skills +PT intervention with non-English speaking participants. Parents must also have internet access to facilitate participating in the remote telehealth DBT Skills +PT intervention. Additionally, eligible parents must endorse elevated emotion dysregulation (a score of >88 on the DERS, equivalent to +.5 SD above a normative score; Ritschel, Tone, Schoemann, & Lim, 2015) and endorse 2 or more items on the CAGE-AID screener for past (past 5 years), but not current (not in the past 12 months), substance use.

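### Partial-custody parents are eligible but days with the child are not recorded, so weekly parenting-skill counts and the WACB mix contact with uptake or child change

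*Combined protocol and SAP*

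**What the plan says.** Section D (Participants) admits parents who "have at least partial custody of a 3-6 year old child". At online screening (section C) parents confirm "that they have at least partial custody of a preschool aged child (3-6 years old)", again with no amount of contact.

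For the Skill Use Diary Card (section C, Materials, item Q), "Parents are asked to circle days of the week in which they used each skill". In addition, "they are asked if DBT Skills were used in a parenting or a non-parenting context"; no such question is described for parenting skills. The same item calls the card a measure of treatment dosage.

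The WACB (Materials, item J) asks "how often their child engages in positive behaviors on a weekly basis".

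Under Analyses, Aim 1, implementation is assessed by "calculating the average daily number of DBT and parenting skills parents report using each week on their diary card", averaged across parents. Under Aim 2, the diary card, WACB, ERC, PS, DERS and DBT-WCCL are read week by week over Weeks 1-20. Visual inspection comes first, then Tau-U, linear regression and hierarchical linear modeling (HLM), for individuals and for the group. No contact denominator, contact covariate or rule for a week without the child is given.

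**The concern.** The eligibility rule itself anticipates shared custody. A parent cannot practise parenting skills with a child who is elsewhere, and has seen little or nothing of that child's week to rate. Without a record of contact, a low parenting-skill count can mean that the skills were not taken up or that the child was away, and the data cannot separate the two. A shift in WACB scores has the same ambiguity.

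Three features of the design make this matter:

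- Parents are plotted individually and the target is 12, so a few shared-custody cases can shape the picture.
- Weekly data start with treatment, after a single pre-intervention assessment. There is no run of earlier weeks in which a custody cycle could be recognised.
- Weekly questionnaires are paid per completion, which favours submitting a rating for a week without the child. If items are skipped instead, they add to the missing-data percentage, which is itself an Aim 1 result.

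Days of contact cannot be recovered reliably once 20 weeks have passed.

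**Working it through.** The plan states no figure on this point, so there is nothing to reproduce. The check has a textual part and an illustrative part.

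**1. Where contact could have been recorded.** The screener asks for confirmation of custody only. The listed demographic items include "number of people in household, number of children, race, ethnicity, socioeconomic status, and religious affiliation", but not custody share or days with the child. The diary card records days of skill use, not days of contact. The weekly battery in Figure 1 has no contact item, and Aim 2 names no contact variable.

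**2. Which weekly measures depend on contact.**

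- Clearly dependent: the diary card's parenting-skill counts and the WACB.
- Less so: the ERC (how characteristic statements are of the child), the PS (how the parent responds to misbehaviour) and the CCNES (hypothetical vignettes). In a week apart these would tend to carry over earlier impressions.
- Not dependent: DERS and DBT-WCCL.

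**3. Level for one parent (assumed values).** Let r be parenting skills used per contact day and c contact days in the week. The planned average is r × c / 7.

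- r = 1: c = 2 gives 2/7 = 0.29; c = 7 gives 7/7 = 1.0.
- r = 2: c = 7, 5, 3.5, 2, 0 gives 2.00, 1.43, 1.00, 0.57, 0.

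Divided by contact days, the result is r for every c above zero, and undefined (not zero) at c = 0.

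**4. Group mean (assumed values).** If k of 12 parents have the child half the time and all share the same r, the planned mean falls short of the per-contact-day mean by (k/12) × 0.5. For k = 3, 6, 12 this is 12.5%, 25%, 50%.

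**5. Trend under alternating weeks (assumed values).** Let true use rise from 1.0 to 2.9 per day over 20 weeks, as 1 + 0.1 × (week − 1). The least-squares slope is 0.10. Trend tau, taken as rising minus falling pairs over 20 × 19 / 2 = 190 pairs, is 1.00. With the 10 weeks without the child entered as zero:

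- child present in odd weeks: slope 0.035, tau 35/190 = 0.18;
- child present in even weeks: slope 0.065, tau 55/190 = 0.29.

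**6. Change of custody (assumed values).** Hold r at 2 throughout, with 2 contact days in Weeks 1-10 and 5 in Weeks 11-20. The planned average moves from 2 × 2/7 = 0.57 to 2 × 5/7 = 1.43. Tau is (10 × 10)/190 = 0.53 and the slope is 50 × (6/7) / 665 = 0.064, although skill use per contact day never changed. Here 50 is the sum of (week − 10.5) over Weeks 11-20, and 665 is the sum of (week − 10.5)² over all 20 weeks.

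**The case against.** The strongest reply has five parts.

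- **The forms are not visible.** The screening script, demographic form, WACB and diary card are appendices that are not in the supplied text, and the Materials section only outlines the measures. A contact or not-applicable item may exist. This stands, and the fix is conditional on it. Even so, the analysis text uses no such item.
- **The planned count is a legitimate quantity.** A parent with two contact days did use fewer parenting skills that week, and for dosage received that is the right number. This stands. A reader might infer that the implementation figure is simply biased downward. It is low only relative to use per contact day, which the plan does not claim to estimate.
- **The plan does not say that weeks without the child score zero.** A reader might infer that it does, but the text is silent either way, so step 5 shows one possible handling. Nor does the diary card, as described, limit parenting skills to the target child; a sibling may be at home.
- **Much of the weekly battery is unaffected.** A reader might infer that PS and ERC ratings from weeks apart are arbitrary and should be dropped. Their described wording does not support that. The expected sequence starts with DBT skill use and parent emotion regulation, neither of which needs the child. The published benchmark named under Aim 1 also concerns DBT skills. The exposure is confined to parenting-skill counts and to the child-behaviour step as read from the WACB.
- **The study is a small pilot, and co-leaders may learn that a child was away.** Homework review and check-ins give them that chance, but the plan does not say it is recorded. This lowers the stakes; it does not close the gap.

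**Conclusion.** The point holds for two measures: the diary card's parenting-skill counts and the WACB. On the text supplied, partial custody suffices, contact is not recorded, and the weekly analyses cannot tell opportunity from uptake or from change in the child. A custody cycle can flatten a real trend, and a custody change can create an apparent one.

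The size cannot be stated. It depends on how many enrolled parents share custody and on their schedules, and the documents give neither. Partial custody need not mean whole weeks apart. Under the assumed patterns, the group mean falls 12.5% to 50% below use per contact day as 3 to 12 of 12 parents have half-time contact; with no such parents the difference is nil.

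The documents do not support a broader conclusion that the whole weekly battery, or the order-of-change analysis as a whole, is compromised. This is an inexpensive improvement to make before data collection.

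**What to change.** Unless the appendix forms already ask it, add one item to each weekly questionnaire set and to the pre- and post-intervention batteries: on how many of the last 7 days was the target child in the parent's care? Then:

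- Keep the planned average daily count as the dosage measure, and add parenting-skill use per contact day as the uptake measure. State whether the card's parenting-skill items refer to the target child only.
- In weeks with zero contact days, treat the WACB and the card's parenting-skill items as not applicable for the uptake and trajectory analyses, and do not count them as missing data in Aim 1.
- Mark contact days on each individual weekly graph, and use them in the HLM as a covariate or in a sensitivity analysis.
- Keep PS, ERC and CCNES in the main analysis, flag their zero-contact weeks, and repeat the analysis without those weeks as a sensitivity check.

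The cost is a few seconds per parent per week, a short scoring rule, and fewer usable WACB and parenting-skill points for shared-custody parents. No one is excluded from the study.

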2. Evaluate pre -post and weekly changes in measures of parental emotion regulation, parenting **stress, parenting quality and children's mental health**. Across all parents enrolled in DBT+PT, we will evaluate the rate and pattern of change in these interlinked domains which represent risk factors for relapse and further adverse outcomes. We anticipate pre-post changes (2 time points, approximately 20-22 weeks apart) will be comparable to well-established change scores from the clinical trial literature base for DBT Skills and parent training interventions. Additionally, qualitative data from exit interviews with each parent will be analyzed using thematic analyses of responses to evaluate parents' perceptions of changes in their own mental health, their parenting and their children's behavior over the course of the intervention.

Weekly repeated measures (20 time points) will allow us to model the rate and pattern of change from week to week. As the intervention is divided into 4 modules (see Procedures), change patterns will also be examined between modules. Data will be presented descriptively and we expect changes to unfold in a cascading order, with increased use of skills preceding reductions in parent emotion dysregulation, followed by improvements in parenting quality and subsequent improvements in child behavior.

C. Methods, Materials and Analysis

Setting. Clinical intakes, the weekly group DBT Skills+PT intervention sessions, and exit interviews will all be conducted via a HIPAA compliant teleconference platform (i.e. Zoom). The initial online screener, and pre-post and weekly assessments will be conducted via UO Qualtrics questionnaires.

Study design. This study utilizes a mixed methods case study design with continuous assessment of quantitative measures. Figure 1 presents the study phases, along with what participating parents will complete in each phase, and the estimated time needed to complete each phase.

	time required of participants.	Time Estimate
Study Phase Recruitment	Participant action Parents respond to recruitment	N/A
Reciditment	materials	
↓		
Initial Online Screener	Parent completes:	
	DERS	DERS – 5 minutes
	CAGE-AID	CAGE-AID – 2 minutes
		Total: 7 minutes
•		
Clinical Intake	Parent completes:	Demographica 4 minutes
_	Demographic questionnaire	Demographics – 4 minutes
	PHQ-9	PHQ-9 - 3 minutes
	PPVT-V (Q-Global) SCID 5 diagnostic interview	PPVT-V – 20 minutes SCID 5– 180-300 minutes
		Total: 207-327 minutes
.		

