We will examine change across time based on data available in the weekly assessment measures of parents' DBT and parenting skill use (DBT-WCCL, Skill Use Diary Card), parents' emotion dysregulation (DERS), parenting quality (PS), and children's symptoms and behaviors (ERC and WACB). Consistent with common practice in case study designs (Kazdin, 2003; Kazdin, 2019; Rizvi & Nock, 2008), we will primarily use visual inspection (i.e. evaluating graphical displays of participants' weekly scores) to examine the data collected during Weeks 1-20 of the DBT Skills +PT intervention. We will use the same procedures to examine changes in data collected at the four time points representing the start of each DBT module. We will inspect several aspects of these data, such as changes in the trajectories of each measure, to determine the direction and extent of change in the measured symptoms and behaviors from week to week, and the timing of when those changes occurred. We will also characterize the order in which changes unfold over time (e.g. increased DBT skill use precedes improvement in parent emotion regulation, which precedes improvements in parenting quality measures, which precedes improvements in child behavior measures). These visual inspection analyses will be conducted at both the individual level and at an aggregated group level.

We will employ a number of standard methods of statistical analysis of single-case experimental design (SCED) data to further examine, quantify and corroborate results of visual inspection. Consistent with previous SCED studies, we will calculate Tau-U effect sizes (Parker et al., 2011; Vannest & Ninci, 2015; Brossart et al., 2018), linear regressions (Ramaiya et al., 2018) and perform hierarchical linear modeling which can be used to aggregate single-case results (Van den Noortgate & Onghena, 2007; Ugille et al., 2012). These analyses will provide preliminary information on the rate and order of change for the different targeted symptoms and behaviors, and enable us to report on the degree to which DBT Skills +PT changed parent-reported symptoms and behaviors at the level of individual parents as well as at the group level, aggregating data across all participating parents.

D. Research Population & Recruitment Methods

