Only one eligible parent can participate in the study. In the case of two parents who wish to participate and both meet inclusion criteria, the family will decide which parent is most likely to complete all assessments and intervention sessions and that parent will be the research participant. If a participating parent has more than one preschool aged child (age 3-6), we will ask parents to decide which child is the target child for whom they will report during assessments. Parents will be excluded if they have a current (past 12 months) substance use disorder, if they do not have a past (past 5 years) substance use disorder, if they or their child have a known developmental disability or if during the clinical intake parents are determined to have a low IQ score (IQ<70) on the PPVT-IV, are psychotic as determined by the SCID 5, actively manic or psychotic as determined by clinical observation, are actively suicidal with an active plan as determined by the SCID 5 and/or PHQ-9, or are determined by clinical judgement to be at high risk of violence towards others. Additionally, if clinical judgement suggests a parent requires a higher level or different form of care, we may exclude them from participating or request that they secure an individual therapy provider in order to participate in the study.

Recruitment. Participants will be recruited through a number of recruitment strategies:

1. Team Duckling (https://teamduckling.uoregon.edu/) developmental database, which is maintained by the UO Psychology Department. Parents of children aged 3-6 will be initially contacted through email using a standard email script (see Appendix B. Recruitment Email).

- 2. Craigslist postings to recruit participants (see Appendix C. Craigslist Posting).
- Social media posts. We may use social media posts/advertisements targeting parents within the state of Oregon (including but not limited to Facebook; for an example, see (Appendix D. Facebook Posting).
- 4. Contacting parents who have participated in previous studies within [name] START Lab or other research labs, and who have indicated they are interested in being contacted to participate in future studies (see Appendix B. Recruitment Email).

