- 5. Referrals from various mental health clinics (including, but not limited to the University of Oregon Psychology Clinic, HEDCO Clinic (College of Education), and the University of Oregon Counseling Center (University of Oregon Health Services), the Child and Family Center (Prevention Science Institute at UO), Portland DBT Insitute, Willamette Family, Serenity Lane, Parenting Now, Vista Counseling, Strong Integrated Behavioral Health. We will provide such clinics with an online virtual flyer with information about the study and a link to our online Qualtrics screener, which they can then provide to clients (see Appendix EE. DBT+PT Recruitment Flier).
- 6. Direct mailings. With the assistance of local agencies (i.e. Department of Human Services, Head Start of Lane County) through which our lab has recruited for previous studies, we will directly mail letters describing our study to the agencies mailing list of families that have children ages 3-6. A recruitment letter (see Appendix FF. Mailing Recruitment) will be provided to the agencies who have agreed to mail the letters on our behalf as to maintain privacy of their clientele. This is a template of what will be stated in the letter. It will be modified slightly (ex. specify agency name) to fit with the population the agency serves.

All recruitment materials will briefly discuss the details of the study and invite parents to complete an initial online screening survey to see if they are eligible to participate.

Parents who pass the initial online screening (see Appendix E. Online Screening Script) will be contacted by a trained research staff member to schedule the diagnostic clinical intake. Parents who do not pass the initial online screening will be thanked for participating and informed that they do not match the eligibility requirements. All parents who complete the online screening will be provided with a list of community mental health resources (see Appendix BB. Community Resources).

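### Outside therapy, which the protocol may request as a condition of entry, is not described as recorded, so its effect cannot be told apart from that of DBT Skills +PT

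*Combined protocol and SAP*

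**What the plan says.** Section D (Participants) closes the exclusion criteria with a discretionary rule. For a parent who seems to need a higher level or another form of care, the team may either exclude the parent or "request that they secure an individual therapy provider in order to participate in the study". Section D (Recruitment) lists six routes, one of which is "Referrals from various mental health clinics".

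On design, Section C states: "This study utilizes a mixed methods case study design with continuous assessment of quantitative measures". There is no comparison arm. The visual analysis is to "examine the data collected during Weeks 1-20 of the DBT Skills +PT intervention", and the full battery is given once before treatment and once after.

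On interpretation, the Analyses section sets out to "evaluate how, when, why, and to what extent the DBT Skills +PT intervention was effective in changing" parent and child outcomes. Under Aim 2, the Tau-U, regression and hierarchical models are meant to let the team "report on the degree to which DBT Skills +PT changed parent-reported symptoms and behaviors at the level of individual parents", and also for the group as a whole. Pre-post change is also to be set against published trials of DBT and parent training.

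Section F (privacy and confidentiality) says that the clinical file, such as session notes and release forms, does not count as study data and is stored apart from it.

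**The concern.** The protocol allows a second treatment to be attached to entry, and it does so selectively, for parents judged to need more care. A case study design rests on documenting the competing explanations for each case. Here one competing explanation can arise from the eligibility rule itself, yet the plan does not say that anyone will write it down as data.

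If outside therapy begins or changes near entry, its effect falls in the same window as the group sessions. A parent's graph could then show a fall in DERS or a rise in DBT-WCCL skill use that comes partly from another provider, and the reader would have no means of knowing. The pilot is also meant to prepare a larger randomized trial, whose planners would want to know how many parents had such therapy. The information is hard to recover once the study has ended.

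**Working it through.** The plan gives no figure on this point to reproduce. The check is a comparison of sections, followed by a calculation for scale.

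**1. Is outside therapy captured by any described measure?** Figure 1 and the Materials list in Section C were read for an item on concurrent treatment.
- Screening and intake (DERS, CAGE-AID, PHQ-9, PPVT, SCID-5): symptoms, use, ability and diagnosis. None is described as recording treatment.
- Demographic questionnaire: the listed contents include no treatment item.
- Outcome scales (HAM-A, ADCS, DBT-WCCL, WACB, CBCL, ERC, PSI, PSOC, PS, CCNES): none concerns outside care.
- Diary card: use of DBT and parenting skills, plus one question on suicidal thoughts.
- CSQ-8 and exit interview: satisfaction, difficulties, skill use and suggestions. The SCID-5 at exit assesses substance use disorder, not its treatment.

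Result: no described measure records whether a parent has outside therapy, when it began or how much was received.

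**2. Could it be found elsewhere?** Session notes or release forms might name a provider, but Section F places them outside the study data.

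**3. Can the design separate it?** There is no comparison arm. The pre-post analysis uses two time points and the weekly analysis covers Weeks 1-20. DERS is also taken at the online screener, but for eligibility; no analysis treats it as part of a baseline series. So there is no planned repeated baseline to show change that came before the group.

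**4. Does any analysis allow for it?** Sections C and D give no rule to describe, flag, adjust for or set aside parents in outside therapy.

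**5. Scale, for illustration.** If k of n parents each gain an extra d SD from outside therapy and the others are unaffected:

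shift in mean change = (k / n) × d

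- n = 12 is the target number completing at least 4 sessions; n = 15 is the maximum enrolled (Section D).
- k = 0 to 4 and d = 0.2 to 0.8 SD are assumptions. The documents give neither.

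| n | k | d (SD) | Shift in mean (SD) |
|---|---|---|---|
| 12 | 0 | any | 0 |
| 12 | 1 | 0.2 | 1 × 0.2 / 12 = 0.017 |
| 12 | 3 | 0.5 | 3 × 0.5 / 12 = 0.125 |
| 12 | 4 | 0.8 | 4 × 0.8 / 12 = 0.267 |
| 15 | 4 | 0.8 | 4 × 0.8 / 15 = 0.213 |

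For a single affected parent there is no dilution. The whole of d, here 0.2 to 0.8 SD, sits in that parent's own result.

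**The case against.** The case against has real force on several points.

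- **Timing.** A reader might infer that the rule makes parents start new therapy near baseline. The text does not say so. It speaks of securing a provider; an existing one might satisfy it, and long-standing therapy may be stable across the 20 weeks. The concern is confined to therapy that begins or changes around entry or during treatment.
- **Frequency.** The rule is discretionary and may touch no one. Clinic referral is one of six routes, so the documents do not show that outside treatment is likely, only that it is possible.
- **Recording.** A reader might infer that outside therapy is recorded nowhere. That goes too far. The demographic form, sample exit questions and release form are listed as appendices but were not available, and a parent may mention therapy unprompted at the exit interview. What can be said is that no described measure records it and no analysis uses it.
- **Attribution.** A reader might conclude that the reported effects would be wrong. The documents support only that they could not be verified for affected parents. Regression to the mean after selection on DERS, the passage of time and child maturation limit attribution for every parent in a one-group design.
- **Ambition.** The plan calls itself a pilot, presents data descriptively and says inferential statistics are not required.

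The last two points do not dispose of the matter. The effect wording in the Analyses section is causal and reaches the individual parent. Unlike maturation or regression to the mean, this influence may be introduced by the protocol and could be documented with very little effort.

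**Conclusion.** The point holds as a gap in data collection and reporting. The protocol may make an outside therapist a condition of entry, no described study measure captures this, and the design cannot separate its effect from the change credited to DBT Skills +PT. The conclusion rests on the measures as described in the body of the protocol; an item in an appendix that was not available would narrow it.

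The size is unknown. Under the assumed ranges, the shift in mean change with 12 parents runs from 0 to 0.27 SD. The individual-level consequence does not depend on how many parents are affected: for each one, all of the added change is credited to the intervention. The direction shown assumes that outside therapy helps. It does not follow that leaving these parents out would lower the group mean, since parents judged to need more care might improve less overall.

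**What to change.** Add two items to the pre- and post-intervention Qualtrics forms:
1. Any individual therapy or substance use treatment, with start date and approximate number of sessions.
2. Whether it was requested as a condition of entry.

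Then state in the Analyses section that the report will:
- give the number of parents affected;
- mark those parents, and the therapy start date, on the individual graphs already planned;
- qualify the attribution of change for them;
- show group pre-post change with and without them, as a descriptive summary only.

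The cost is about one minute per assessment, against listed totals of 64 minutes before and 129 minutes after the intervention. No visit, staff or procedure is added. The drawback is that the with/without contrast will be imprecise in a sample this small. It is also confounded by severity, because the request goes to parents judged to need more care, so it should not be read as an estimate of the therapy's effect. The clinical rule itself is left as it is.
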